Statistical Analyses: We will analyze the LH pulse frequency data from the tanner stage 1-3 normal girls and the LH pulse frequency data from the tanner stage 4-5 normal girls, by way of a linear-mixed effects ANCOVA model. The response variable will identify the change in the LH pulse frequency between the LH pulse frequency measured at the first overnight admission (baseline) and that measured at the second overnight admission (after progesterone supplementation). The ANCOVA model will include one independent factor and two independent continuous covariates. The independent factor will identify the girl's tanner stage (1-3, or

Assessment of the sensitivity of the hypothalamic GnRH pulse generator to estradiol and progesterone inhibition in early pubertal girls (JCM026)

4-5), while the two independent continuous covariates will identify the girl's progesterone levels at baseline and following estradiol and progesterone supplementation. Based on the parameter estimates from the ANCOVA model, we will be able to compare the magnitude of the change in LH pulse frequency after estradiol and progesterone supplementation between the two groups of girls after adjusting for the girls' progesterone concentration following estradiol and progesterone supplementation (overnight admission 1) and after adjusting for the girls' progesterone concentration following estradiol and progesterone supplementation (overnight admission 2). A generalized-F-test will be utilized to formally test the null hypothesis that estradiol and progesterone supplementation alters LH pulse frequency in tanner-stage 1-3 girls to the same degree as in normal tanner-stage 4-5 girls. The decision rule to reject the null hypothesis, will be based on a P≤0.05 criterion. Confidence interval construction, for estimating the true group to group difference in the percentage change in LH pulse frequency after estradiol and progesterone supplementation, will be base on the Students t-distribution multiplier. The PROC MIXED procedure of SAS version 9.1.3 EAS (SAS Institute Inc, Cary NC) will be used to conduct the aforementioned statistical analyses.

In order to ensure an adequate sampling of younger girls, no more than 4 enrolled subjects will be Tanner stage 3. The number of subjects in each Tanner stage will be reported with the final results.

What is the primary outcome variable upon which a sample size estimate is based?

Do I have an adequate sample size, or is my sample size larger than necessary? *The calculation of sample size also allows the CRU to properly budget for adequate resources to help you complete your proposal.*

Risk/ Benefit Analysis:

What are the potential benefits for the participant as well as benefits which may accrue to society in general, as a result of this study?

Although individual subjects will not benefit from participating in this study, the results will advance our knowledge of normal pubertal maturation. A better understanding of normal pubertal maturation may lead to insights regarding abnormal pubertal maturation (e.g. precocious puberty) or disorders with pubertal onset (e.g. PCOS). Hopefully this research will translate into improved prevention and treatment for these disorders in the future.

Analyze the risk-benefit ratio:

This study involves minimal risks, but may provide valuable information about normal pubertal maturation and the origins of PCOS. PCOS is the most prevalent reproductive disorder in young women and typically manifests at puberty. Enhanced understanding of normal neuroendocrine function during puberty and how these normal processes go awry in PCOS will be essential to design rational prevention and treatment strategies for PCOS. Therefore, we feel the potential benefits to society are substantial while the risks to the participants are quite small.

Data and Safety Monitoring Plan

Note: A Sponsor-is defined as entity that will receive data prior to publication.

1. Definition:

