The PI and co-investigators have extensive experience in studies of the early manifestations and abnormalities of pubertal maturation during research over the past 25 years. Much of this research has involved joint collaboration with colleagues in the Department of Pediatrics, and this continues in the present application with co-investigators in the Dept. of Pediatrics. These individuals are specialists in pediatric endocrinology and are well versed and have expertise in dealing with children of the age ranges included. The group currently has 8 ongoing, IRB-approved studies in the adolescent population, including 6 that involve overnight admissions with frequent blood sampling. Over 100 girls to date have enrolled in overnight studies.

B. Study Support

This study will be supported by NIH funds through the General Clinical Research Center Core Grant and through a U54 Specialized Cooperative Centers Program for Research in Reproduction and Infertility (IRB# 9112)

Assessment of the sensitivity of the hypothalamic GnRH pulse generator to estradiol and progesterone inhibition in early pubertal girls (JCM026)

C. International Research

Will this study be done outside the U.S. under the oversight of a UVA PI? NO

D. Has another IRB ever not given approval to this protocol?

Drug Information

• Micronized progesterone powder (Spectrum Chemical Manufacturing Corporation, Irving, CA), IND# 64,126

No

• Estrace (Warner-Chilcott, Rockaway, NJ)

Please list the phase or stage of this study. Not applicable. **Does this study involve research on a drug, biologic, supplement or food additive?** Yes If yes, is this study investigator initiated? Yes

If yes, answer questions # 1 and 2

If no, answer question # 2 only.

1. Do the following criteria apply?

No The investigation is intended to be reported to FDA as a well-controlled study in support of a new indication for use or intended to be used to support any other significant change in the labeling for the drug;

No If the drug that is undergoing investigation is lawfully marketed as a prescription drug product, the investigation is intended to support a significant change in the advertising for the product;

No The investigation does involve a route of administration or dosage level or use in a patient population or other factor that significantly increases the risks (or decreases the acceptability of the risks) associated with the use of the drug product.

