Criteria for inclusion:

- Girls ages 8 to 14
- Tanner 1-3 pubertal stage
- Pre-menarchal
- Normal screening labs

Criteria for exclusion:

- Abnormal screening labs
- congenital adrenal hyperplasia.
- Hyperandrogenism (e.g., hirsutism, elevated free testosterone level)
- Hemoglobin <11.5 g/dL for non-African American subjects; Hemoglobin < 11.0 g/dL for African American subjects
- Weight < 31 kg
- History of peanut allergy, deep venous thrombosis, breast cancer, endometrial cancer, or cervical cancer
- On hormonal medications (including oral contraceptive pills) or on medications known to affect the reproductive axis within 3 months of the study
- Pregnant or breast feeding
- Participation in a research study within the past 30 days that involved taking a study drug.
- Participation in a research study that involved taking up to or greater than 473 ml's of blood within the past 60 days.
- Cigarette smoking
- History of surgery that required bedrest within the past 30 days
- Family history of hypercoagulability or unexplained thromboembolic disease (not in setting of bedrest, surgery, or malignancy)

Assessment of the sensitivity of the hypothalamic GnRH pulse generator to estradiol and progesterone inhibition in early pubertal girls (JCM026)

• In order to ensure an adequate number of younger girls, no more than 4 enrolled subjects will be Tanner stage 3

Restrictions (if any) **on use of other drugs or treatments:**

Subjects must discontinue all hormonally-active medications at least 3 months prior to the frequent sampling study (and 2 months prior to screening visit) and must not take any other medications known to affect the reproductive axis during the study. There are no dietary requirements for this study.

Recruitment

How will participants be recruited?

- _X__ Posters/Flyers
- _X__ Television
- X Radio
- X Newspaper Ads
- X_____ Internet
 - Medical Record/ Database Review. NOTE- potential subjects will be contacted after obtaining the approval of their attending physician and IRB-HSR approval of method of contacting potential subjects (i.e. letter)
 - ____ Medical Record/ Database Review. NOTE- subjects will not be contacted
 - X___ Referrals from other health care professionals
- X Discuss protocol with patients of PI or sub-investigators during a standard clinical visit

If subjects will be contacted, explain in detail how this will be done.

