Assessment of the sensitivity of the hypothalamic GnRH pulse generator to estradiol and progesterone inhibition in early pubertal girls (JCM026)

physical, screening blood tests) occurs immediately thereafter. Participants generally begin the main part of the study within 1-2 months of the screening visit.

Do you plan to enroll your own students, patients, staff, employees? Yes.

Do you plan to enroll students, patients, staff, employees of any of the other personnel listed on this protocol? Yes

Do you plan to enroll yourself or any other personnel listed on this protocol? No

If yes, which groups? Subjects may be recruited from Dr. [name]'s, Dr. [name]'s, Dr. [name]'s, Dr. [name]'s, and Dr. [name]'s clinical practices. However, Drs. [name], [name], rarely if ever see early pubertal girls in their clinics. It is also possible that the children of our clinic patients, students, or employees may be enrolled. We will not enroll children of study investigators.

If yes, explain how these potential subjects will be recruited to avoid the appearance of coercion.

Patients who appear to be appropriate candidates for this study will be made aware that they may qualify for participation in the study. If they express interest, we will offer a very brief explanation of what is involved. If the patient continues to express interest, we will give them our research coordinator's contact information. In keeping with our mandate as physicians, we will discuss the study only in instances where potential participation would not be harmful to the patient (e.g. in cases where temporarily withholding customary treatments is expected to have no harmful effects). Subjects will be informed that their participation in the study is entirely voluntary and their decision whether or not to participate will have no effect on their current or future medical care.

Biomedical Research

List what will be done in this protocol:

All procedures performed in this protocol are being done solely to answer a research question and generate generalizable knowledge.

Outpatient Screening

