The subject will be admitted to the CRU, alternate UVA hospital unit, or off-site hotel at ~1700 hr. In general, parents are welcome to stay with their child at the off-site hotel if they wish. If the overnight portion of the study is to be done at an off-site hotel, the subject may stay without a parent or legal guardian, as long as two CRU staff are present. Whether or not a parent needs to remain during the overnight admission will be discussed when the visit is scheduled. A urine b-HCG will be performed to rule out pregnancy and must be negative for the study to continue. A small amount of topical lidocaine/prilocaine cream (EMLA cream) may be applied to facilitate IV line placement. An IV line will be placed in a forearm or hand vein and blood draws will begin at 1900 hr. Samples will be taken every 10 minutes. Most samples will be 0.75 mL, used to analyze levels of FSH and LH. 2.5 mL samples will be taken every 2 hours to analyze levels of estradiol, progesterone, testosterone, cortisol and DHEA An additional 3.0 mL sample will be analyzed for fasting insulin, Insulin-like Growth Factor 1 (IGF-1), fasting glucose, estrone, sex hormone binding globulin, DHEA-S, androstenedione and a number of cytokines and adipokines, including adiponectin, leptin, resistin, PAI-1, IL-1b, IL-6, IL-8, TNFa, MCP-1, HGF and NGF. (Due to new technologies adipokines and cytokines can be measured in a total of 25 ul of serum, thereby allowing us to measure these without substantially increasing the necessary blood volume).

A formal "lights out" will occur at 2300 hr so that we may observe any nocturnal changes in LH release patterns. Q10 minute blood sampling will end at 0600 hr. There will be one final blood draw at 0700 hr. During blood sampling, activity (e.g., awake, sleeping) will be recorded by the nurse every 10 minutes. Additionally, periods of sleep will be estimated using wrist actigraphy (Motionlogger Basic-L; Ambulatory Monitoring, Inc.). The Motionlogger Basic-L is a watch-like device (that includes an accelerometer) that will be worn on the wrist by the research participant during overnight admission. The subject will be offered meals at standard CRU meal times.

Day 1: Study medications

Starting the day of discharge from the first inpatient admission, subjects will be given oral estrogen (estrace, 0.5-1 mg once a day) and oral progesterone suspension (20 mg/ml, 25-100 mg) three times a day at

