Assessment of the sensitivity of the hypothalamic GnRH pulse generator to estradiol and progesterone inhibition in early pubertal girls (JCM026)

Frequency unknown
Occurs frequently,
Occurs infrequently
Occurs rarely
Frequency unknown
Occurs frequently,
Occurs infrequently
Occurs rarely
Frequency unknown
Occurs frequently,
Occurs infrequently
Occurs rarely
Frequency unknown

Risk associated with iron supplementation

Expected Risks related to study participation-	Frequency		
iron supplementation	Please pick one frequency from each box below		
• nausea	Occurs frequently,		
	Occurs infrequently		
	Occurs rarely		
	Frequency unknown		
constipation	Occurs frequently,		
-	Occurs infrequently		
	Occurs rarely		
	Frequency unknown		
dark or black stools	Occurs frequently,		
	Occurs infrequently		
	Occurs rarely		
	Frequency unknown		

Risk associated with EMLA cream (topical lidocaine and prilocaine, used to alleviate pain): The risks of lidocaine and prilocaine in general may include (frequency not defined) hypotension, angioedema, shock, hyperpigmentation, erythema, itching, rash, burning, urticaria, burning, stinging, edema bronchospasm, and hypersensitivity reactions. However, in the case of topical lidocaine/prilocaine use, the non-dermatologic adverse events mentioned above would be extremely unlikely unless large amounts of topical lidocaine/prilocaine were used (allowing significant systemic absorption).

Risk regarding wrist actigraphy: There are no known risks associated with the use of wrist actigraphy.

Risk of not being able to take hormonal medications: Fertility in premenarcheal girls is exceedingly unlikely. Thus, the risk of pregnancy related to inability to take hormonal birth control medication is virtually absent.

- 2.2 List by bullet format a summary of safety tests/procedures/observations to be performed.
 - Sterile technique will be used.
 - Before participation in the study, all participants will be required to have a normal hemoglobin (≥ 11.0 g/dl for African American subjects or ≥ 11.5 g/dL for non-African American subjects). Hemoglobin levels will be measured prior to every admission, and the admission will only continue if the

Assessment of the sensitivity of the hypothalamic GnRH pulse generator to estradiol and progesterone inhibition in early pubertal girls (JCM026)

hemoglobin level is ≥ 11.0 g/dl for African American subjects or ≥ 11.5 g/dL for non-African American subjects.

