- Blood loss will be carefully recorded and limited to a maximum of 7cc/kg (10% of estimated total blood volume) in 8 weeks. A total of 216.5 ml of blood will be drawn during the study (including estimated waste from frequent blood draws). Therefore, girls weighing less than 31 kg will not be able to participate. Iron supplementation (325 mg once or twice a day dependent on weight) will be prescribed to all participants.
- β -hCG levels will be measured at screening and prior to each admission; if the β -hCG is positive, the study will be discontinued.
- Topical lidocaine and prilocaine (EMLA) cream may be used to lessen pain associated with IV needle insertion.
- 2.3 Check the criteria below under which an INDIVIDUAL SUBJECT'S study treatment or study participation would be stopped or modified

At subject, PI or sponsor's request

Treatment would be stopped if the subject had a Serious adverse event deemed related to study

The study would be stopped in the patient has a positive pregnancy test or a hematocrit <36 and hemoglobin <12 prior to any of the 4 admissions.

2.4 Check the criteria under which THE ENTIRE STUDY would need to be stopped. These are called stopping rules for early termination of the entire study.

⊠Per IRB, PI, DSMB, or sponsor discretion

 \bigcirc Other: If there are an excessive number of unexpected adverse events that significantly alter the risk/benefit ratio for the study, the study will be terminated. All adverse events will be evaluated both individually and cumulatively by the study team and principal investigator as they arise, allowing for timely decisions regarding study continuation/termination.

- 2.5 Describe the criteria for breaking the blind/mask 🖾 NA Not blinded/masked
- 2.6 How will subject withdrawals/dropouts be reported to the IRB prior to study completion?☑ IRB-HSR continuation status form

3. Adverse Event / Unanticipated Problem Recording and Reporting

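### The exclusion for prior research blood sets no working volume threshold; the protocol's own 7 mL/kg, 8-week limit should replace it

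*Combined protocol and SAP*

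**What the plan says.** All references are to the combined protocol and SAP.

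- **Inclusion/Exclusion Criteria.** One exclusion reads "Participation in a research study that involved taking up to or greater than 473 ml's of blood within the past 60 days". A separate one reads "Participation in a research study within the past 30 days that involved taking a study drug". The list also excludes girls under 31 kg, and girls on hormonal or reproductive-axis medication within 3 months of the study. The paragraph on drug restrictions repeats the 3-month rule for hormonally active medication and counts it back from the frequent sampling study.
- **Data and Safety Monitoring Plan, 2.2.** Blood loss is "limited to a maximum of 7cc/kg (10% of estimated total blood volume) in 8 weeks". The plan continues: "A total of 216.5 ml of blood will be drawn during the study", waste included, and derives the 31 kg floor from these two figures. It adds: "Hemoglobin levels will be measured prior to every admission".
- **Recruitment, consenting process.** "Participants generally begin the main part of the study within 1-2 months of the screening visit".
- **Additional Information, A. Investigators Experience.** The group reports "8 ongoing, IRB-approved studies in the adolescent population, including 6 that involve overnight admissions with frequent blood sampling".
- **Biomedical Research, Day 0.** Sampling is every 10 minutes from 1900 to 0600 hr, with one last draw at 0700. "Most samples will be 0.75 mL, used to analyze levels of FSH and LH". There are also 2.5 mL samples every 2 hours and one additional 3.0 mL sample. The second admission follows the same procedure.

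**The concern.** An eligibility threshold should sort girls into eligible and ineligible. This one does not, because it names volumes below 473 mL as well as volumes above it. Staff must choose a reading, and a girl with a modest recent research draw is ineligible on one and eligible on the other.

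The reading that gives 473 a purpose (at least 473 mL) is a fixed adult-sized volume, whereas the safety plan scales its limit to body weight. The two do not fit together for light girls, and the weight floor leaves almost no slack.

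The criterion also does not say from which date the 60 days run. The main study generally starts 1-2 months after screening, and the Outpatient Screening section foresees gaps of more than 3 months. For such gaps it repeats hemoglobin and safety labs but states no new check of research blood drawn elsewhere.

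At stake is the blood-volume limit for healthy girls aged 8 to 14 who gain no individual benefit from taking part. The primary comparison is not at stake.

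**Working it through.** **Inputs.** Cap 7 mL/kg in 8 weeks, study draw 216.5 mL and floor 31 kg (Data and Safety Monitoring Plan, 2.2); 473 mL and 60 days (Inclusion/Exclusion Criteria); sample volumes and times (Day 0).

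**1. Reproduce the plan's own figure.** Minimum weight = 216.5 / 7 = 30.93 kg, rounded up to 31 kg. It reproduces, and it uses this study's blood alone.

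**2. Compare 473 mL with the cap.**
- Cap at 31 kg: 7 × 31 = 217 mL.
- 473 / 31 = 15.3 mL/kg; 473 / 217 = 2.18 times the cap.
- Weight at which 473 mL equals the cap: 473 / 7 = 67.6 kg. Below that weight, 473 mL alone exceeds the cap before this study draws anything.
- Weight at which 473 mL plus the full study draw fits: (473 + 216.5) / 7 = 98.5 kg.

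**3. Study blood that must fall in one 8-week window.** The 216.5 mL is not itemised, and screening may fall outside the window, so a range is needed. From 1900 to 0600 hr every 10 minutes there are 11 × 6 + 1 = 67 samples.
- Low (six 2.5 mL samples replace 0.75 mL samples, and the 3.0 mL sample is the 0700 draw): 61 × 0.75 + 6 × 2.5 + 3.0 = 63.75 mL.
- High (seven 2.5 mL samples and the 3.0 mL sample are all additional): 67 × 0.75 + 7 × 2.5 + 3.0 = 70.75 mL.
- Two admissions: 127.5 to 141.5 mL.

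This is a lower bound. The Day 3 and Day 5 draws fall between the admissions and waste arises during sampling, so both always add to it.

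**4. Room for prior research blood** (7 × weight − study blood).

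| Weight | Cap | All 216.5 mL in the window | Two admissions only (upper bound, not reachable) |
|---|---|---|---|
| 31 kg | 217 mL | 0.5 mL | 75.5-89.5 mL |
| 35 kg | 245 mL | 28.5 mL | 103.5-117.5 mL |
| 40 kg | 280 mL | 63.5 mL | 138.5-152.5 mL |

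**5. Illustration** (assumption: 100 mL drawn by another study in the same 8 weeks, girl of 31 kg). Remaining room is 217 − 100 = 117 mL, less than the 127.5 mL lower bound for the two admissions. Her total would be at least (100 + 127.5) / 31 = 7.3 mL/kg and at most (100 + 216.5) / 31 = 10.2 mL/kg. A smaller prior draw, such as one overnight session on this protocol's schedule (63.75 to 70.75 mL), exceeds the room on the full count but lies inside the unreachable upper bound. The documents cannot settle that case.

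**6. Windows.** Eight weeks is 56 days, so a 60-day look-back is long enough if it is counted from Day 0. If it is checked only at screening, a draw between screening and Day 0 is missed on either reading.

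**The case against.** The strongest reply is that the words as written protect the child. Taken literally, any research blood in the past 60 days excludes her, and 60 days is longer than 8 weeks. This stands: the conflict with the cap arises only on the at-least-473 reading. It does not rescue the criterion, because staff cannot tell from the page which reading applies, and the missing start date affects both.

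Second, the same list holds another safeguard. The 3-month exclusion for hormonal and reproductive-axis medication bars girls who took estradiol and progesterone in an earlier sampling study, well beyond 8 weeks. This also stands, and it narrows the exposure to sampling studies without such drugs. The 30-day study-drug exclusion does not reach those that give no drug, or draws made more than 30 days earlier. The statement about six overnight studies does not say how many give no hormones or enrol girls like these, so the remaining exposure is possible but cannot be quantified.

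Third, the cap is a binding limit on blood loss, and its sentence is not expressly confined to this study. It could be read to include other research blood. The text is silent, however, and the floor is derived from this study's draw alone. If inclusion was intended, the entry criterion still needs to agree with it.

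Fourth, the hemoglobin requirements before each admission, the one-month validity rule and the iron supplements lower the risk of anemia. They do, but they do not enforce a volume.

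Finally, a simpler edit would do: exclude any research draw within 60 days of the first admission. That would close most of the gap, at the price of excluding girls whose small draws fit within the cap.

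A reader might infer that the plan lets a 31 kg girl lose 473 + 216.5 = 689.5 mL, 3.18 times the cap. That takes the looser reading, ignores the cap as a limit on conduct, and needs another study to draw nearly half a litre from a small child. Nothing in the documents suggests such a study.

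**Conclusion.** The criterion sets no working threshold, and the only reading that gives 473 mL a function is inconsistent with the protocol's own cap: 2.18 times the cap at 31 kg, and above it for every girl under 67.6 kg. These figures rest on stated numbers only. The room left for prior blood at 31 kg is 0.5 mL if the whole 216.5 mL falls in 8 weeks. The true figure could be higher if screening falls outside the window, but it stays below 75.5-89.5 mL.

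The practical exposure is limited to sampling studies without hormonal drugs and to draws shortly before Day 0 if eligibility is checked only at screening. This is a worthwhile safety correction of modest weight.

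Two stronger inferences are not supported. The documents show no girl in this study with such a prior draw, so no breach can be claimed, and nothing links this point to the LH pulse endpoint, the sample size or the power. Nor can it be said that repeat screening labs of up to 5 mL push a 31 kg girl over the cap, because the documents do not show whether those labs are already inside the 216.5 mL.

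**What to change.** 1. In Inclusion/Exclusion Criteria, replace the 473 mL item with: *Excluded if blood drawn for any other research study, plus the blood drawn and planned under this protocol, would exceed 7 mL/kg of current body weight in any 8-week period through the second admission; if the prior volume is unknown, defer the first admission until 8 weeks after that draw.* Check it at screening and again on Day 0.
2. In the Data and Safety Monitoring Plan, 2.2, add after the cap: *Blood drawn for any other research study in the same 8 weeks counts toward this limit.*

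The 31 kg floor stays. A girl with no other research blood remains under the cap that already applies to her.

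The cost is a short amendment with one reworded criterion and one added sentence. Staff must ask about and document prior research draws twice, and families may not know the volume. Some lighter girls may wait up to 8 weeks. Compared with the literal reading, some girls with small prior draws become eligible, still within the cap.
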